- 2) The fake (placebo) Erchonia® EVRL is designed to have the same physical appearance as the actual Erchonia® EVRL, including the appearance of any visible and invisible light output. Therefore, both the test and placebo devices emit light when activated that is indistinguishable to both the subject and to the investigator. As the laser light does not put out any notable degree of heat or noise, these are not distinguishing factors for subjects between the two groups.

RANDOMIZATION

Subject randomization occurs following attainment of subject consent. Subject allocation to treatment group will be via variable block randomization with varying block sizes of two, four and six used at random to minimize the likelihood of predicting the next treatment group assignment.

Randomization will be attained using computer generation sequence methodology, ensuring that the randomization methodology and the generated allocation sequence is concealed from the subjects.

Concealment will be insured as follows:

- (ii) Each computer-generated randomization sequence is unique and will therefore not be able to be replicated.
- (iii) Randomization will occur to either 'Treatment Group A' or to 'Treatment Group B' rather than to a test or placebo group, and only one designated individual at the Sponsor site will know which assignment (A or B) corresponds to the active device and which corresponds to the fake device. Unblinding will not occur until the final study data set analysis is complete.

SUBJECTS

Recruitment

Subjects will be recruited from online advertisements for individuals who have been previously diagnosed with diabetes induced peripheral neuropathy by a suitably qualified and licensed health professional.

Compensation

A subject who completes his or her participation in this clinical study through to the final post-treatment administration will receive financial compensation of \$200.

A subject will not be charged for the cost of the study treatments with the Erchonia® EVRL Laser or for the cost of any other directly-related evaluations or measurements that occur as part of his or her participation in the study.

Sample size

There will be 64 qualified subjects enrolled in this clinical study:

32 subjects in the active treatment group
32 subjects in the po treatment group

Rationale for sample size

Based on the following parameters established for the purposes of assessing efficacy of the Erchonia® EVRL in this clinical study ...:

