- Individual subject success criteria defined as a 30% or greater reduction in self-reported Degree of Pain rating on the 0-100 VAS from baseline to study endpoint evaluation.

N.B.: The clinical relevance of a 30% change in VAS score is explained and supported in the STATISTICAL ANALYSIS PLAN section further along in this protocol document.

- Overall study success criteria of at least a 35% difference between the active device group and the placebo device group, comparing the proportion of individual successes in each group.
- It is anticipated that about 55% of subjects in the active device group and about 20% of subjects in the placebo device group will meet the individual success criteria, and
- intended application of a two-tailed test with an alpha value of 0.05 and Power of 0.8

...the sample size of 29 subjects per group (active group and placebo group, separately) has been determined using the following reference calculator: *Hypothesis Testing: Categorical Data - Estimation of Sample Size and Power for Comparing Two Binomial Proportions* in Bernard Rosner's *Fundamentals of Biostatistics*.

For the purposes of sample size calculation, it is anticipated that about one-twentieth of subjects overall may withdraw from the study prior to completion for various reasons. Therefore, the following formula is used to determine the final needed starting sample size for each group:

Final sample size = sample size X 1/(1-d); where d = # expected dropouts/# subjects enrolled.

Final sample size = 29 X 1/(1-0.083)

Final sample size = 29 X 1/0.917 = 29 X 1.0905 = 31.62, rounded to 32 subjects per treatment group.

Therefore, a minimum starting sample size of 32 subjects in each treatment group is needed to ensure that sufficient numbers remains at the end of the trial (29 subjects per group) for any significant differences found between groups to be considered statistically valid and representative of the general population being sampled. This results in a total of 64 subjects being enrolled in this study across both study treatment groups.

STUDY PROCEDURE

STUDY TEST BATTERY

The following are the study assessment tools to be used and the variables to be recorded in this clinical study.

BASELINE VARIABLES

A. Neuropathy Variables

- Number of months/years since onset of foot pain.
- Number of months/years since diabetes diagnosis
- Insulin dependency

B. Medication and Treatment

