- If using analgesics (pain medication), must be on a stable analgesic regimen (i.e., no changes to the prescribed analgesic regimen) over a period of at least 14 days prior to enrollment; and willing and able to not have planned upward dose titration of analgesics during the study period. The subject may elect to decrease analgesic use during the study. Cannabis prescribed for medicinal purposes would qualify as an analgesic in this context.
- Willing and able to refrain from engaging in any non-study procedure therapies for the management of foot pain throughout the course of study participation, including conventional therapies such as physical therapy, occupational therapy and hot or cold packs, as well as alternative therapies such as chiropractic care and acupuncture.
- Agrees to refrain from taking a dosage of analgesic (pain medication) for at least 6 hours before a scheduled VAS foot pain rating is to be recorded.
- Subjects' degree of foot pain on the 0-100 VAS, with "0" being no pain and "100" being worst pain imaginable, is 50 or greater.

EXCLUSION CRITERIA

A subject who satisfies any of the following criteria will be excluded from study participation:

- Pregnant or think they might be pregnant.
- Open wounds (sores, cuts, ulcers, etc.) around the feet
- Cancerous growths around the feet.
- Difficulty with hand dexterity sufficient to impact ability to administer treatments with the laser such as from severe arthritis in the hands, Multiple Sclerosis, Cerebral Palsy, Parkinson's Disease, Huntington's Disease, etc.

PRE-TREATMENT EVALUATION PHASE

The pre-treatment evaluation phase commences following successful study qualification.

BASELINE VARIABLES

- Baseline Foot Variables
- Medication and Treatment
- Insulin Dependency
- Subject Demographics

PRE-TREATMENT OUTCOME ASSESSMENTS

- Visual Analog Scale (VAS) Degree of Foot Pain Rating
- Neuropathic Pain Symptom Inventory (NPSI)

The Pre-Treatment Outcome assessments will serve as the Baseline data set.

AT-HOME TREATMENT ADMINISTRATION PHASE

A fully qualified enrolled subject will be provided either a Erchonia® EVRL A or B device based on his or her randomization to treatment group (see Randomization). Additionally, the enrolled subject will be provided the EVRL Proper Use Reference Guide (**Appendix D**) and applicable Case Report Forms (**Appendix M**) for capturing study outcome assessments.

TREATMENT ADMINISTRATION PROTOCOL

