3 WEEK EVALUATION: STUDY ENDPOINT

Following completion of the entire 3 weeks of study treatment administrations with the Erchonia® EVRL, the following will be recorded on the provided case report forms by the subject at home as outlined in the STUDY TEST BATTERY section above. These recordings will form the study endpoint data set from which change from baseline will be evaluated with respect to assessing study outcome

- Visual Analog Pain Scale (VAS) Degree of Foot Pain Rating
- Neuropathic Pain Symptom Inventory (NPSI)
- Subject Satisfaction With Study Outcome
- Perceived Treatment Group

POST-TREATMENT ACTIVITIES

7 WEEK EVALUATION: 4 Weeks Post-Treatment

Four weeks following the completion of the 3-week treatment administration phase, the following will be recorded on the provided case report forms by the subject at home, as outlined in the STUDY TEST BATTERY section above.

- Visual Analog Pain Scale (VAS) Degree of Foot Pain Rating
- Neuropathic Pain Symptom Inventory (NPSI)
- Subject Satisfaction With Study Outcome
- Perceived Treatment Group

COMPLIANCE ASSESSMENT LOG

The subject will record each day when they have administered a treatment with the Erchonia® EVRL Laser.

CHANGE IN MEDICATION RECORD SHEET

If at any time during the treatment and/or post-treatment administration phases the subject has a change in his or her medication use (cessation of prior medication, change in dosage/frequency of use of a current medication, addition of a new medication) the subject will record the medication name, dose/frequency of use, expected duration of medication use, and the reason for the change in the Change in Medication Record Sheet.

ADVERSE EVENTS

It is unlikely and not expected that any adverse events will result from implementation of this clinical study protocol. Prior clinical trials using low level laser light have not typically yielded any adverse events or reactions. However, potential adverse events that may feasibly occur from application of the Erchonia® EVRL include, but are not necessarily limited to skin irritation, discoloring, rash, indentations, and infection.

PRIVACY AND CONFIDENTIALITY

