 - *Positive blinding efficacy* will be supported through qualitative assessment of comments provided to support perceived group assignment that pertain to the determination being based on treatment efficacy or lack thereof, e.g.: 'My foot pain is much less than it used to be, so I believe I got the real treatment' or 'My foot pain hasn't really changed, so I believe I got the fake treatment.'
 - *Blinding will be determined to have failed* if comments provided to support perceived group assignment pertain to factors such as sensation/visual clues or overhearing conversations by research staff members.

INDIVIDUAL SUBJECT VAS RATINGS ACROSS STUDY DURATION

Individual subject data for the Primary Outcome Measure of diabetic peripheral neuropathy foot pain VAS Ratings as recorded at each of Baseline (pre-treatment) and Study Endpoint (Week 3) assessments, by Treatment Group, by Test Site, will be presented in table format.

INDIVIDUAL TEST SITE DATA

Key demographic and neuropathy variables and the primary outcome assessment for the ITT analysis population will be presented by treatment group by each of the four individual test sites participating in this study. Data will be presented in descriptive format only due to the small sample sizes that preclude statistical conclusions from being validly drawn.

SAFETY ANALYSES

Safety analyses will be based on all subjects who were randomized to the test or to the placebo treatment group. Safety will be assessed by evaluating and comparing frequency and incidence of observed and/or reported adverse events between test and placebo treatment groups. A chi-square test with a continuity correction will be performed to compare the percentage of subjects who had adverse events between test and placebo treatment group subjects.

INFORMED CONSENT

- Informed consent will be an agreement between the individual investigator and each subject, having the capacity to understand and make an informed decision. Consent will be obtained prior to each potential subject's participation in this clinical study.

- Each subject participating in this clinical study will be made aware of the fact that his or her participation involves research and the intent of the research, the expected duration of his or her participation and a description of the procedures that will be followed.
- Each subject will be made aware of the reasonably expected benefits he or she might receive, as well as any risks or potential discomfort that are involved.

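### Safety is counted over everyone randomised, including subjects never given a device, and its only inference is a test with no interval that has low power for modest excesses at 32 per arm

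*Combined protocol and SAP*

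**What the plan says.** The Safety Analyses section sets the population: "Safety analyses will be based on all subjects who were randomized to the test or to the placebo treatment group". It then describes the comparison: "Safety will be assessed by evaluating and comparing frequency and incidence of observed and/or reported adverse events between test and placebo treatment groups". The one inferential step follows: "A chi-square test with a continuity correction will be performed to compare the percentage of subjects who had adverse events". The section gives no significance level for this test, no confidence interval and no rule for sparse or absent events.

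Three other places matter:

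- Subject Randomization to Treatment Group assigns subjects to A or B once consent is signed, before eligibility is evaluated.
- At-Home Treatment Administration Phase limits who receives a device: "A fully qualified enrolled subject will be provided either a Erchonia® EVRL A or B device".
- Adverse Events sets the expectation: "It is unlikely and not expected that any adverse events will result from implementation of this clinical study protocol".

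**The concern.** The denominator does not match exposure. A subject who is randomised, fails qualification and never receives a device cannot have a device-related event, yet counts as event-free in the incidence.

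The inference is also poorly matched to the data that the plan expects. The plan foresees few or no events. With none, the chi-square statistic cannot be calculated; with few, it seldom reaches significance. Without an interval, the report would show counts and perhaps a non-significant p-value, and nothing on how large a harm the data leave open. The device is self-administered at home 42 times over three weeks, so what a small exposed group can and cannot exclude is the useful safety information.

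**Working it through.** **Inputs.** 32 per arm comes from Sample size ("32 subjects in the active treatment group") and its rationale ("a minimum starting sample size of 32 subjects in each treatment group is needed"). The plan's own figure reproduces. For 55% vs 20%, two-sided 0.05 and power 0.80, the mean proportion is 0.375 and n = [1.960·√(2·0.375·0.625) + 0.842·√(0.55·0.45 + 0.20·0.80)]² / 0.35² = 28.8, so 29. Then 29/(1 − 0.083) = 31.6, so 32. That calculation is for efficacy; no figure is given for safety. Alpha of 0.05 two-sided is an assumption borrowed from the efficacy design ("intended application of a two-tailed test with an alpha value of 0.05 and Power of 0.8"). All adverse event rates below are assumptions, because the plan states none.

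**Step 1: denominator.** With e events, T treated and R randomised in an arm, reported incidence is e/R = (e/T)·(T/R). For e = 6 and T = 32, true incidence among the exposed is 6/32 = 18.8%. The ratio T/R is not given, so a range is shown:

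| Randomised per 32 treated | Reported incidence |
|---|---|
| 32 (no failures) | 18.8% |
| 36 | 6/36 = 16.7% |
| 40 | 6/40 = 15.0% |
| 48 | 6/48 = 12.5% |

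An upper limit is affected too. With zero events the exact two-sided 95% limit is 1 − 0.025^(1/n): 10.9% for n = 32, but 8.8% for n = 40, although only 32 were exposed.

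**Step 2: the test at 32 per arm.** With a and b events, Yates chi-square = N(|a(n−b) − b(n−a)| − N/2)² / [n·n·(a+b)(N−a−b)], with n = 32 and N = 64.

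- 0 vs 0: the denominator is zero, so there is no result. If the true rate were 1% in both arms this would happen with probability 0.99^64 = 53%; at 2%, 0.98^64 = 27%.
- 5 vs 0: 64·(160 − 32)² / (1024·5·59) = 3.471, p = 0.062. Fisher p = 0.053.
- 6 vs 0: 64·(192 − 32)² / (1024·6·58) = 4.598, p = 0.032. Fisher p = 0.024. This is the smallest significant split when placebo has no events.

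For 5 vs 0 the Newcombe 95% interval for the difference is +1.8 to +31.8 points.

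**Step 3: power.** Binomial probabilities were summed over all pairs of counts with p < 0.05 and more events on active:

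| True rate, active vs placebo | Corrected chi-square | Fisher |
|---|---|---|
| 10% vs 0% | 9% | 9% |
| 15% vs 0% | 35% | 35% |
| 20% vs 0% | 64% | 64% |
| 25% vs 0% | 85% | 85% |
| 15% vs 5% | 11% | 11% |
| 20% vs 5% | 28% | 28% |
| 30% vs 5% | 68% | 68% |

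**Step 4: do the two problems compound?** Hardly. With 40 randomised per arm, 5 vs 0 gives 80·(200 − 40)² / (1600·5·75) = 3.41, p = 0.065, against 0.062 at 32. Dilution distorts the reported incidence and its limits, not the test.

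**The case against.** A reader might infer that a harmful device would almost always be reported as showing no difference. The documents do not support that. The test finds an excess of 20% vs 0% in 64% of trials and 25% vs 0% in 85%. The section also compares frequency and incidence by group, so a 5 vs 0 split would be visible. No text says that a non-significant result will be read as safety.

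Nor is the corrected test a plain error. Fisher's exact test, a standard choice for sparse tables, gives almost the same results, so the main limit is 32 per arm. The uncorrected test has more power (40% at 10% vs 0%) and would flag 4 vs 0 (p = 0.039), but the expected event count is then only 2 per arm. A Newcombe interval that excludes zero beside p = 0.062 sets a less conservative method against a more conservative one; it does not show a mistake. With no events at all, a missing p-value leads to no wrong conclusion.

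On the denominator, the Sample size section speaks of 64 qualified subjects, no screen-failure rate is given, and similar dilution would be expected in both arms.

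All of this stands and limits the point. It does not remove two gaps: the written population rule conflicts with the order of randomisation and device supply, and counts without an interval do not show what they leave unexcluded.

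**Conclusion.** The point holds in limited form. The all-randomised rule puts never-exposed subjects into the incidence. The size depends on an unstated failure rate: nil if nobody fails after randomisation, and 18.8% read as 15.0% if 40 are randomised per 32 treated. The single planned inference has no result at zero events and low power for modest excesses: 9% to 35% for 10 to 15 points above a zero placebo rate, and 11% to 28% for 10 to 15 points above 5%. Large excesses would usually be found.

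These figures rest on exactly 32 per arm, alpha 0.05 for the safety test, and assumed event rates. The primary efficacy result is untouched. This is a worthwhile correction to the safety reporting; it does not show that harm would be concealed.

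**What to change.** In Safety Analyses:

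1. Define the safety set as subjects who self-administered at least one treatment, grouped by the device used. List separately those randomised but never treated.
2. Make the main safety summary the incidence per arm with exact (Clopper-Pearson) 95% intervals, and the between-arm difference with a 95% interval that works with zero cells, such as Newcombe. This takes the place of the corrected chi-square test.
3. State that a non-significant difference will not be reported as evidence of safety.

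The cost is SAP wording and a few lines of code, with no extra subjects or visits. The compliance log, in which subjects record their treatments, can identify the exposed. The downside is a slightly less favourable statement: zero events in 32 would be reported with an upper limit of 10.9%. The change does not raise power; it makes the limits of 32 per arm visible.
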